6.1.4.2. Withdrawal Endpoint

Withdrawal Endpoint is defined as the last non-missing post-withdrawal baseline assessment in the withdrawal period (regardless of clinic or non-clinic visits).

6.1.5. Aggregated Analysis Timepoint

An aggregated analysis timepoint named as ‘any OL treatment period (treatment emergent)’ will be derived for selected safety assessments (eg, the worst case analysis) as below.

- Any OL treatment period (treatment emergent): defined as any assessment collected in open-label treatment period (see [Section 6.1.1.1](#)).

Specifically, the aggregated analysis timepoint of any OL treatment period (treatment emergent) will be applied on the following worst-case analysis:

- Markedly Abnormal Laboratory Values (MALV) ([Section 7.4.3.1](#), [Table 6](#))
- Markedly Abnormal Vital Signs (MAVS) ([Section 7.4.5.1](#), [Table 9.1](#))
- QTc prolongation ([Section 7.4.4.1](#), [Table 7](#))
- ECG abnormality ([Section 7.4.4.1](#), [Table 8](#)).
- C-SSRS ([Section 7.4.7](#))

6.1.6. Pooling Strategy for Analysis of Centers

There will be no pooling of centers in this study.

6.1.7. Adjustments for Covariates

Not Applicable. No statistical modeling or inference will be performed, including the ones containing baseline as a covariate to adjust baseline.

6.1.8. Analysis Populations

The Safety Population: All subjects who receive at least one dose of study medication. The safety population mainly is used for the data analyses of the safety data collected through Week 52 or during the open-label treatment period.

The Withdrawal Population: The withdrawal population includes all subjects who receive at least one dose of study medication, and either early terminate from the study drug during the OL treatment period or complete the 52-week OL treatment period, and have at least 1 assessment after the last study drug for any evaluation. The withdrawal population is used to summarize the safety and effectiveness assessments collected in the withdrawal period. Withdrawal analysis will be presented by analysis group.

The ‘Modified’ Withdrawal Population: all subjects in the withdrawal population plus the subjects who either are early terminated during the OL treatment period or complete the 52-week OL treatment period and do not enter the withdrawal period, but the last study dose dates are at least 2 days prior to their last study visit. The modified withdrawal population will be only used for summary of adverse event data which could be retrospectively collected.

6.1.9. Analysis Group and Analysis Subgroup

For all subjects in Study 360-322, summary tables, wherever applicable, will be presented by analysis group per subject’s previous participation in core studies (ie, subjects previously randomized to dasotraline, subjects previously randomized to placebo, all subjects combined) as described as below

- Pbo-Das: Subjects previously randomized to placebo in studies SEP360-221 or SEP360-321
- Das-Das: Subjects previously randomized to dasotraline group in studies SEP360-221 or SEP360-321
- All-Das: all subjects combined

For subjects continued from Study SEP360-221, analyses per selected data may be conducted as needed; summary of these analyses will be presented per subject’s previous participation in study SEP360-221 as described below (hereafter, referred as ‘Analysis Subgroup A’):

- Pbo-Das: previously randomized to placebo
- Das-Das: previously randomized to dasotraline 4–8 mg/day
- 221-Das: all subjects continued from study SEP360-221

For subjects continued from Study SEP360-321, analyses per selected data may be conducted as needed; summary of these analyses will be presented per subject’s previous participation in study SEP360-321 as described below (hereafter, referred as ‘Analysis Subgroup B’):

- Pbo-Das: previously randomized to placebo
- Das4-Das: previously randomized to dasotraline 4 mg/day
- Das6-Das: previously randomized to dasotraline 6 mg/day
- AllDas-Das: previously randomized to dasotraline (4 mg/day or 6 mg/day)

322

- 321-Das: subjects continued from study SEP360-321

Subjects in Study SEP360-322 may be further grouped and presented according to their predominant dose (alternatively, modal dose, see [Section 6.1.10](#)) and the maximum dose during the open-label treatment period as below, as needed. Hereafter, analysis subgroup based on the modal dose will be referred as ‘Analysis Subgroup C’ and analysis subgroup based on the maximum dose will be referred as ‘Analysis Subgroup D’.

Analysis Subgroup C

- Das4: subjects with modal dose of dasotraline 4 mg/day
- Das6: subjects with modal dose of dasotraline 6 mg/day
- Das8: subjects with modal dose of dasotraline 8 mg/day
- All Das: all subjects combined

Analysis Subgroup D

- Das4: subjects with maximum dose of dasotraline 4 mg/day
- Das6: subjects with maximum dose of dasotraline 6 mg/day
- Das8: subjects with maximum dose of dasotraline 8 mg/day
- All Das: all subjects combined

For limited analyses, wherever applicable, results may be presented by modal dose group and maximum dose group as needed.

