4.3. Risk-Benefit Assessment

Overall, in previous clinical studies dasotraline was generally safe and well tolerated. The pharmacokinetic (PK) and safety profiles observed in adults from completed clinical studies support evaluation of dose levels of 4 - 8 mg/day in adults with BED.

Most adverse events in completed clinical studies were mild to moderate in intensity, and included headache, dizziness, insomnia, tachycardia, and nausea. Dose dependent increases in the incidence of insomnia and weight loss were observed, consistent with DNRI pharmacology. A total of 13 serious adverse events (SAEs) have been reported in 9 subjects receiving dasotraline. Across the 8 completed clinical studies evaluating dasotraline, the rate of discontinuations as a result of treatment-emergent adverse events (TEAEs) was low. The highest rate of discontinuations due to TEAEs was in the SEP360-201 adult ADHD study (11.2% and 29.7% of subjects treated with dasotraline 4 and 8 mg/day, respectively), primarily due to insomnia. In general, the side-effect profile of dasotraline, based on available data, appears comparable with other medications used in the treatment of ADHD and suggests it may be well tolerated in patients with BED. A flexible dose design to reach the 8 mg dose will be implemented in this study to facilitate management of safety and tolerability issues.

The results from the human abuse liability study indicate dasotraline has minimal abuse potential and is unlikely to be recreationally abused. All doses of dasotraline (8, 16, 36 mg) demonstrated significantly lower drug liking scores than methylphenidate (40, 80 mg) and were no greater than placebo. The most frequently reported abuse potential adverse events were insomnia and dizziness in subjects with major depressive disorder (MDD) and insomnia and suicidal ideation in adults with ADHD. The current study will be conducted in accordance with relevant regulatory guidance and law with regards to handling, distribution, storage, dispensation, accountability, and destruction of study drug. In addition a comprehensive Abuse Potential Monitoring Plan (APMP) for dasotraline designed to detect potential abuse of the compound and to more closely monitor adverse events (AEs) consistent with the pharmacology of the compound will be implemented for this study (Section 24, Appendix V).

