10.1.2. Dose Adjustment Criteria

The total daily dose will remain between 4 mg/day and 8 mg/day for the 12-month treatment period. Dasotraline will be dosed at 4 mg/day for the first 2 weeks of the study. At the Week 2 visit, the dose may be increased to 6 mg/day. Thereafter the dose may be increased or decreased by 2 mg/day, as necessary for effectiveness or tolerability reasons at the discretion of the investigator. A minimum of 8 days is required between dose increases. Dose decreases may be made at less than 8 day intervals, at the investigator's discretion, for reasons of safety or tolerability. If, in the judgment of the investigator, the subject does not tolerate the minimum required dose (4 mg/day), he or she will be discontinued from the study.

All changes in study drug dose will begin the morning after the visit at which the dose change decision is made and using the new package of study drug.

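### Displays of AEs or discontinuation by modal or maximum dose over the whole open-label period can hide or reverse a dose-related signal, because the dose group depends on how long a subject stayed on drug

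*SAP*

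**What the plan says.** Protocol 10.1.2 fixes the dose path. The start is the same for everyone: "Dasotraline will be dosed at 4 mg/day for the first 2 weeks of the study". The rule for the first possible increase is: "At the Week 2 visit, the dose may be increased to 6 mg/day". After that, steps are 2 mg, and "A minimum of 8 days is required between dose increases". The start of a new dose is also fixed: "All changes in study drug dose will begin the morning after the visit at which the dose change decision is made". Step-downs are less restricted: "Dose decreases may be made at less than 8 day intervals". A subject who cannot tolerate 4 mg leaves the study.

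SAP 6.1.9 defines four analysis subgroups. A and B follow the core study. C uses the modal dose and D the maximum dose, both over the open-label treatment period. SAP 6.1.10 defines modal dose as the dose with the longest exposure, and ties go to the higher dose. Use of C and D is optional: "Subjects in Study SEP360-322 may be further grouped and presented according to their predominant dose", and for limited analyses "results may be presented by modal dose group and maximum dose group as needed".

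SAP 7.1.2 presents disposition, and the Kaplan-Meier plot of time to early discontinuation, by analysis group and subgroup. It does not say whether C and D are included. The AE summaries in SAP 7.4.2 are by core-study arm (Pbo-Das, Das-Das, All-Das). Its subgroup tables are by age, gender, race and BMI, and its exposure tables are by time interval, not dose. No landmark, minimum exposure, dose-at-onset rule or caution is attached to C or D.

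**The concern.** Modal and maximum dose are known only after follow-up. To enter a higher group, a subject must first have stayed on the lower doses long enough, which is immortal-time bias. Early stoppers collect in Das4 whatever dose they were heading for. Under the modal rule, some events that occurred on 6 mg are counted against 4 mg. An early event at 4 mg in a subject later raised to 8 mg is counted against Das8. The titration rules push the same way: intolerance at 4 mg ends treatment, whereas above 4 mg a step-down is possible.

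Dose matters to this programme. Protocol 4.3 reports discontinuation for AEs in the adult ADHD study as "11.2% and 29.7% of subjects treated with dasotraline 4 and 8 mg/day, respectively", and dose-dependent insomnia and weight loss. C and D are the only groupings by extension dose that the SAP defines. If they are used for outcomes, a flat or inverse pattern could be read as reassurance about 8 mg when titration produced it.

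**Working it through.** The plan states no figure to reproduce here; the study is descriptive. The check has three parts.

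**1. Classification, from the plan's rules on nominal visit days.** The Week 2 visit is Day 14, so 6 mg starts on Day 15. The Week 4 visit is Day 28, so 8 mg starts on Day 29.
- Stop on Days 1-14: Das4 by both rules.
- Stop on Day d in 15-27 while on 6 mg: 14 days at 4 mg against d - 14, at most 13, at 6 mg. Modal Das4, maximum Das6. On Day 28 the tie (14 = 14) goes to 6 mg.
- Stop on Days 29-41 while on 8 mg: at most 13 days at 8 mg, with 14 each at 4 and 6 mg. Modal Das6, maximum Das8.
- Modal Das8 first occurs on Day 42 (14 + 14 + 14).
- With an unscheduled visit, 8 mg could start on Day 23 (15 + 8). Stops on Days 23-35 while on 8 mg are then modal Das4, and modal Das8 needs Day 36.

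A maximum-dose Das8 discontinuation curve therefore cannot fall before Day 29 (Day 23 at the earliest).

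**2. Possible size.** Assumptions, none from the documents: 80% go to 6 mg on Day 15, 60% of those still on drug go to 8 mg on Day 29, and AE discontinuation is the only exit to Day 364. On each path, e(t) = S(t) × h(t) × HR(dose on day t) and S(t+1) = S(t) - e(t).

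Worked case: maximum dose, no dose effect, h = 0.003/day to Day 28 and 0.0005/day after.
- Survival of Days 1-14 is 0.997^14 = 0.9588, and the same for Days 15-28. Survival of Days 29-364 is 0.9995^336 = 0.8453.
- Das4: N = 0.0412 + 0.2 × 0.9588 = 0.2330. Events = 0.0412 + 0.1918 × (1 - 0.9588 × 0.8453) = 0.0775. Share 33.3%.
- Das6: of 0.8 × 0.9588 = 0.7670 starting 6 mg, 0.0316 stop on Days 15-28 and 0.4 × 0.7354 = 0.2942 stay on 6 mg. Events = 0.0316 + 0.2942 × 0.1547 = 0.0771. Share 0.0771/0.3258 = 23.7%.
- Das8: 1 - 0.8453 = 15.5%.

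All cases, % discontinued for AE in Das4/Das6/Das8:

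| Hazard | True HR at 6, 8 mg | Maximum dose | Modal dose |
|---|---|---|---|
| Front-loaded | 1, 1 | 33.3/23.7/15.5 | 40.8/16.9/14.9 |
| Front-loaded | 1.5, 2 | 33.3/33.2/28.5 | 43.8/24.6/27.6 |
| Constant 0.0006/day | 1, 1 | 22.2/20.0/18.3 | 24.5/19.3/17.6 |
| Constant 0.0006/day | 1.5, 2 | 22.2/28.4/33.2 | 25.6/27.9/32.1 |

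A second check used the ADHD figures: ln(1 - 0.297)/ln(1 - 0.112) = 2.97 as the 8 v 4 mg hazard ratio. Day-by-day simulation assumed HR 1.72 at 6 mg, a 4 mg hazard of 11.2% over 364 days and other dropout of 0.1%/day. The percentage with an AE event was:
- First-28-day hazard tripled, intended doses 10/30/60% at 4/6/8 mg, half of AEs above 4 mg handled by step-down: modal 32.9/22.3/18.2 (reversed), maximum 19.2/19.8/23.9 (nearly hidden).
- Mildest case (equal thirds intended, titration finished by Week 4, no early excess, no step-down): modal 11.2/15.6/23.3, maximum 10.3/15.6/23.9. The order is correct, with 8:4 ratios of 2.1 and 2.3.

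**3. Does dose at onset do better?** A smoothly falling hazard is a hard test: h(t) = 0.0004 + 0.004e^(-t/20), same titration. Rates are events at a dose divided by subject-days at that dose, × 36,525, per 100 person-years.

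| Interval | No dose effect, 4/6/8 mg | HR 1.5, 2 |
|---|---|---|
| Days 1-28 as one block | 109.0/65.6/none | 109.0/98.4/none |
| Days 14-27 | 72.4/66.7/none | 72.4/100.1/none |
| Days 28-83 | 27.1/27.7/26.7 | 27.1/41.7/53.5 |

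From Day 84 the no-effect rates are equal across doses. A single Day 28 split still misleads in the first block. The SAP's narrower intervals largely remove the problem.

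**The case against.** The strongest reply is about scope. C and D are optional, SAP 7.4 names no AE table by either, and SAP 7.1.2 does not say which subgroups its plot uses. The objective is the safety of the flexible regimen in an uncontrolled, descriptive study, not dose-response. That stands. A reader might infer that the primary safety tables are biased. The documents do not support this, because those tables are by core-study arm.

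The second reply is about size. A reader might infer that C and D will necessarily hide the signal, or that a flat pattern could only come from titration. That is also unsupported. The large distortions need an early excess of events, slow continuing titration or step-downs, and the documents give no such patterns. All subjects completed a core study, and those from the dasotraline arms continue without a break, so early clustering may be confined to former placebo subjects. With front-loading only in an assumed one-third from placebo and hazard ratios of 1.5 and 2, maximum dose gives 24.3/27.3/28.7%, in the right order. Modal dose remains distorted at 30.5/24.2/27.8%.

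The third reply is that dose at onset is imperfect. Protocol 4.2 gives a half-life of 47.1 to 77.0 hours, so exposure lags the dose, and titration is not randomised. Both points stand as limits of the alternative. Neither supports using C or D for outcomes.

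**Conclusion.** The classification follows from the plan's own rules and needs no outside assumption beyond visits on nominal days. Any display of AEs or discontinuation by C or D can therefore hide or reverse a dose-related signal. Across the scenarios above, the result runs from a false inverse gradient (40.8/16.9/14.9% by modal dose with no dose effect) to a correctly ordered pattern. Where a given study falls depends on titration and early-AE patterns that the documents do not state. Modal dose is usually the more distorted rule. The weakness is confined to optional dose displays and, if C or D is used there, to disposition and the discontinuation plot in SAP 7.1.2. It is worth correcting because the SAP attaches no caution and a better method can be built from data already collected.

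**What to change.** - In SAP 6.1.9, limit modal and maximum dose to describing exposure, as in 7.1.5.1.
- In SAP 7.1.2, state that disposition and the time-to-discontinuation plot are not shown by C or D. State the same for AE outcomes in 7.4.2.
- If safety by extension dose is shown, assign each TEAE, SAE, AESI and AE leading to discontinuation to the dose taken at onset. Divide by subject-time at that dose. Present results within the existing exposure intervals (1-13, 14-27, 28-83, 84-167 and 168 days or more) and compare doses only within an interval.
- Add rules for events near a dose change, given the half-life, for events after the last dose, and for incomplete dosing dates. On the last, SAP 6.1.10 drops visits with incomplete kit data, while 7.1.5.1 accepts reported dates and amounts without card return. Reconcile the two.
- Note that titration is not randomised, so the comparison remains descriptive.

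The cost is SAP wording and modest programming. Dosing dates, dose amounts and AE onset dates are already collected. Some cells will be thin, and Days 1-13 can show 4 mg only.

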6.1.10. Average Dose, Predominant/Modal Dose, Maximum Dose

The predominant dose (or, equivalently, modal dose, used interchangeably hereafter in this document) duration in the open-label treatment period is defined as the dasotraline dose to which the subject was exposed for the greatest duration during the treatment period. If a subject has 2 or more doses with the great duration, the one with higher dosage will be selected as predominant treatment.

The average total daily dose during the open-label treatment phase will be calculated as the sum of the total daily dose divided the treatment duration (see [Section 7.1.5.1](#)). The average total daily dose during a visit period is defined in a similar way.

For any study visit, if medication kit usage information is incomplete (ie, meet one of following conditions: any dispensed medication kit at the visit has missing number of tables returned, or has missing dosing start or ending date), average total daily dose at the visit will not be derived and will be set as missing. For an assessment period that involves multiple study visits (eg, the open-label treatment period), if at some visit(s) the drug usage information is incomplete, then

the other visits with complete information of kit usage will be used to derive the average daily dose, predominant dose, and maximum dose, accordingly.

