7.1.5. Study Medication and Concomitant Medications

7.1.5.1. Study Medication

Descriptive summary statistics (N, mean, median) for the mean daily dose will be provided by analysis group at each post-baseline visit, endpoint, and overall treatment period. Mean daily dose for an assessed period (eg, overall treatment period) will be calculated as the sum of the total daily dose divided by the total exposure (ie, last dose day – first dose day+1) in the assessed period.

In addition, frequency distribution of the following dose information will be summarized:

322

- predominant dose(ie, modal dose) during the open-label treatment period
- maximum daily dose during the open-label treatment period

See [Section 6.1.10](#) for definition of the predominant daily dose during the OL treatment period.

In addition, frequency distribution of the all dispensed medication (regardless the kit return status) by study visit and number and percentage of subjects who have modified the dosing schedule since last visit will be summarized by visit.

Return of the blister card at any given visit is not a prerequisite for inclusion in average daily dose summary statistics or predominant dose summary statistics if corresponding dose start and end dates and amount are reported.

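### SAP 6.1.10 discards a recorded dose when one returned count is missing; this conflicts with SAP 7.1.5.1 for modal (and possibly average) dose and can understate maximum dose

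*SAP*

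**What the plan says.** SAP 6.1.10 calls kit information at a visit incomplete if "any dispensed medication kit at the visit has missing number of tables returned", or if a dosing start or end date is missing. For such a visit, "average total daily dose at the visit will not be derived and will be set as missing". For a period that spans several visits, "the other visits with complete information of kit usage will be used to derive the average daily dose, predominant dose, and maximum dose". Modal dose is the dose with the longest exposure; in a tie, "the one with higher dosage will be selected as predominant treatment".

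SAP 7.1.5.1 takes a different line: "Return of the blister card at any given visit is not a prerequisite for inclusion in average daily dose summary statistics or predominant dose" summaries, "if corresponding dose start and end dates and amount are reported". That sentence does not name maximum dose, although the same section tabulates it. The section plans that "mean daily dose will be provided by analysis group at each post-baseline visit, endpoint, and overall treatment period", with the sum of daily doses "divided by the total exposure (ie, last dose day – first dose day+1) in the assessed period".

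Each section points to the other: 6.1.10 to 7.1.5.1 for treatment duration, and 7.1.5.1 to 6.1.10 for the definition of predominant dose. Neither says which rule prevails. SAP 7.1.4 counts exposure days without card return when dates are reported. SAP 7.1.3 uses the same incompleteness trigger as 6.1.10 for compliance, where tablets taken are dispensed minus returned.

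**The concern.** When a card is not returned and its count is missing, but strength and dosing dates are recorded, one section drops the whole visit and the other keeps it. A programmer could follow either and comply with the SAP, yet produce different tables.

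The returned count is essential to compliance. It is not needed to know which strength a subject was on, because each dose is one capsule of 4, 6 or 8 mg (Protocol 9.1 and 10.1.1). Under 6.1.10 the same days can count as exposure in 7.1.4 while the dose recorded for them is discarded.

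At stake are the planned summaries of mean daily, modal and maximum dose in 7.1.5.1, and any optional table by Subgroup C (modal dose) or D (maximum dose). The exposed subjects are those with only one or two visits at their highest dose, for example because they stopped early or their dose was later reduced.

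**Working it through.** The plan gives no figure to reproduce, so the check compares the two rules and then applies them to assumed subjects.

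**The rules side by side**

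| Situation at a visit | SAP 6.1.10 | SAP 7.1.5.1 |
|---|---|---|
| A dosing date is missing | Visit excluded | Allowance does not apply; no conflict |
| Count missing, dates and strength recorded: modal dose | Visit excluded | Visit kept |
| Same: average dose | Visit excluded | Visit kept, unless *amount* means a returned count |
| Same: maximum dose | Visit excluded | Silent |

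**Inputs**

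- Visits at Weeks 2, 4 and 8, so intervals of 14, 14 and 28 days, with a dose change starting the morning after the visit (Protocol 7.1 and 10.1.2).
- Two or four blister cards per dispensing visit (Protocol 9.4).
- Average dose = sum of daily doses / days. Modal dose = dose with most days, ties to the higher dose. Maximum = highest dose among the visits used.
- Assumed: the subjects themselves, no missed doses, dates and strength recorded, and a kit equal to one card (the SAP does not define kit).

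**Subject 1**: 4 mg on Days 1–14, 6 mg on Days 15–28, 8 mg on Days 29–56, then stops. One card from the last interval has no count.

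- All visits kept (7.1.5.1, with *amount* read as strength): average = (14×4 + 14×6 + 28×8)/56 = 364/56 = 6.5 mg/day. Modal = 8 mg (28 days against 14 and 14).
- Last visit excluded (6.1.10): average = (56 + 84)/28 = 140/28 = 5.0 mg/day. Modal = 6 mg, by the tie rule on 14 against 14 days. Maximum = 6 mg, although 8 mg was recorded.
- If the excluded days stayed in the denominator, which 7.1.5.1 writes as last minus first dose day plus 1, the average would be 140/56 = 2.5 mg/day.

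**Subject 2**: 364 days, with 4 mg for 14 days, 6 mg for 322 days and one 28-day interval at 8 mg without a full count.

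- All visits kept: (56 + 1,932 + 224)/364 = 2,212/364 = 6.08 mg/day; modal 6 mg; highest recorded dose 8 mg.
- 8 mg interval excluded: 1,988/336 = 5.92 mg/day; modal 6 mg; maximum 6 mg.

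Over a full year the average barely moves and the mode does not, but the maximum still falls by one class.

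**Direction.** The highest dose among a subset of visits cannot exceed the highest among all visits. Exclusion therefore leaves maximum dose unchanged, lowers it, or blanks it if no complete visit remains. Modal dose can move either way. With 4 mg for 56 days then 6 mg for 28 days, an uncounted card in the Week 4–8 interval leaves 28 against 28 days, and the tie rule raises the mode from 4 to 6 mg.

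**The case against.** The strongest reply is that the sections address different things: 6.1.10 turns on a missing data field, 7.1.5.1 on physical return of the card. The parallel sentence in 7.1.4 asks only for dates, so *amount* was added where dose is derived. If it means quantity taken, an unreturned card with a reported quantity is kept and one without is dropped, and the sections largely coexist. This stands for average dose: if the sum of daily doses means capsules actually taken, a count is arguably needed. It is weak for modal dose, which is defined by duration at each dose and makes no use of a count. The SAP does not define the word.

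It is also fair that maximum dose involves no contradiction. There is one explicit rule, and the complaint is that it discards a recorded dose. On the denominator, taking numerator and denominator from the same visits is the natural reading, and 2.5 mg/day lies below the lowest strength, so a programmer would probably notice it.

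A reader might go further and infer that the Kaplan-Meier plot of early discontinuation in SAP 7.1.2 is distorted because subjects are grouped by a dose reached after baseline. The documents do not support that. The subgroup there is unnamed, Protocol 15.3.4 plots the curve by analysis group, SAP 4 declares no change from the protocol, and Subgroups C and D are optional. A reader might also infer that many subjects would be misclassified. The documents give no rate of missing counts, dropout or titration from which to estimate that.

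**Conclusion.** The point holds as a minor one. The two sections conflict for modal dose, and for average dose unless *amount* means a returned count. For maximum dose, the only stated rule can report a lower dose than the one recorded.

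In the worked cases the shift is one dose class (8 to 6 mg) for maximum dose, one class for modal dose in the 56-day subject and none in the 364-day subject, and 1.5 or 0.16 mg/day for average dose. These are constructed subjects; how many real ones would be affected is unknown.

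The reach is limited to the descriptive dose summaries in 7.1.5.1 and any optional Subgroup C or D table. Adverse event, laboratory and effectiveness tables by analysis group are untouched, and no hypothesis is tested. Two displays let a reader gauge the loss: dispensed medication by visit regardless of kit return (7.1.5.1) and the counts of incomplete kits (7.1.3).

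**What to change.** - In SAP 6.1.10, derive modal and maximum dose from dispensed strength and dosing dates whenever these are reported, counting an end date imputed under 6.1.11.1 as reported.
- Add maximum dose to the card-return sentence in 7.1.5.1.
- For average dose, state one rule in both sections and define *amount*. If a visit is still excluded, say that its days leave the denominator too.
- Keep the returned-count rule for compliance in 7.1.3.

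The cost is SAP wording and modest programming before the final database lock, with no new data, since dispensed strength is already to be tabulated regardless of return. The downside is that modal and maximum dose would then reflect dispensed rather than counted capsules, and for subjects lost to follow-up would rest on an imputed end date, which fixes the length of their last interval. A footnote on the dose tables should say so.
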